3.6 Determination of sample size

Sample size will be based on the proportion of clinical success of therapy in the two groups. Two previous studies conducted at ICDDR,B evaluated efficacy of erythromycin in the management of cholera in children. In one of them, the rate of occurrence of clinical success (resolution of diarrhoea) within 96 hours of initiation of therapy was 95% of the children who received 12.5 mg/kg of erythromycin suspension every 6 hours for 3 days (the dose that will also be used in this study) [39]. We expect that the rate of clinical success with a single dose of azithromycin will be similar to that of erythromycin. Thus, using the methods of Makuch and Johnson [37] for equivalence studies, we calculated the sample size as follows:

$$n = 2 \times P \times (1-P) \times (Z_{\alpha} + Z_{\beta})^2 / d^2$$

where:

P is the overall proportion of success (95%)

Z_{α} is the upper tail point of the standard normal distribution (1.645)

d (0.10) is the maximum difference in the upper 95% confidence limits

(100 x (1 - α)% for the difference in success in two treatment groups with the probability of (1 - β).

Based on the above equation we estimate a sample size of 58 patients in each treatment arm, or a total of 116 patients, with a type I error of 5% and a type II error of 20%. To account for patients whose admission stool cultures are negative for *V. cholerae* O1 or O139, or who prematurely withdraw from the study, we estimate that about 160 patients will be required to be initially enrolled in order to obtain 116 patients evaluable for analysis, however, enrollment will continue until 116 patients evaluable for analysis are obtained.

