DESCRIPTION OF THE RESEARCH PROJECT

Hypothesis to be tested:

Concisely list in order, in the space provided, the hypothesis to be tested and the Specific Aims of the proposed study. Provide the scientific basis of the hypothesis, critically examining the observations leading to the formulation of the hypothesis.

The hypothesis of this study is that in the treatment of cholera due to *V. cholerae* O1 or O139 in children aged 1-15 years, a single, 20 mg/kg dose (maximum of 1.0 gram) of azithromycin suspension will be as effective as the conventional, 3-day, multiple dose therapy with erythromycin suspension administered in a dose of 12.5 mg/kg (maximum individual dose of 500 mg) every 6 hours.

Specific Aims:

Describe the specific aims of the proposed study. State the specific parameters, biological functions/ rates/ processes that will be assessed by specific methods (TYPE WITHIN LIMITS).

The specific aims of the protocol are as follows:

1. Primary Aim

The primary aim of this study is to compare the clinical as well as bacteriologic efficacy of a single, 20 mg/kg dose (maximum of 1.0 gram) of azithromycin oral suspension with the conventional 3-day, 12.5 mg/kg (maximum individual dose of 500 mg) 6 hourly dose of erythromycin oral suspension in the treatment of clinically severe cholera in children due to *V. cholerae* O1 or O139.

2. Secondary Aims

The secondary aims of this study are:

- 2.1 To determine the serum and stool concentrations of both study drugs at specified times, and also to determine their serum half-lives.
- 2.2 To determine the minimum inhibitory concentration of *V. cholerae* O1 and O139 to the study drugs.
- 2.3 To monitor and compare the incidence, type and severity of adverse events in association with the study drugs.

Background of the Project including Preliminary Observations

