4.1 Primary outcome measures

- Rates of clinical success
- Rates of bacteriologic success

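### For clinical success, 58 per arm does not deliver 5% type I and 20% type II error together: limits that hold about 5% have about 70% power, and the second primary outcome is unsized

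*Protocol*

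**What the plan says.** Protocol section 3.6 rests the calculation on one outcome: "Sample size will be based on the proportion of clinical success of therapy in the two groups". It takes 95% success with erythromycin from an earlier study at the same centre and assumes no true difference: "We expect that the rate of clinical success with a single dose of azithromycin will be similar to that of erythromycin". It uses a normal-approximation formula from a method for equivalence studies, with 1.645 as the critical value. It describes the margin thus: "d (0.10) is the maximum difference in the upper 95% confidence limits". From this, "we estimate a sample size of 58 patients in each treatment arm, or a total of 116 patients", with 5% type I and 20% type II error.

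The Primary Aim is wider than the outcome that was sized: "The primary aim of this study is to compare the clinical as well as bacteriologic efficacy". Section 4.1 accordingly lists clinical success and, beside it, "Rates of bacteriologic success". The protocol gives no expected rate, margin or power for bacteriologic success.

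**The concern.** At 95% success, 58 patients give 58 × 0.05 = 2.9 expected failures per arm. The formula treats the observed difference as normal with a well-estimated variance, and that is weak with so few failures. If the approximation fails, the promised 5% and 20% may not both be met.

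The practical stake is how a miss would be read. If true power is nearer 70% than 80%, an equally good single dose misses the margin about 3 times in 10 instead of 2, and the miss could be taken as evidence of a worse drug. If the simple limit is used to keep the 80%, a drug that is worse by the full margin passes more often than 5% of the time.

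Separately, a reader may take the 80% and 5% to cover the whole primary aim, although only one of its two outcomes was sized.

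**Working it through.** **Inputs (section 3.6).** P = 0.95 in both arms, d = 0.10, Zα = 1.645 (one-sided 5%), type II error 20% (Zβ = 0.8416), equal allocation.

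**The plan's figure.** n = 2P(1−P)(Zα+Zβ)²/d² = 2 × 0.95 × 0.05 × (2.4866)² / 0.01 = 58.74, or 59 rounded up. Power on the same approximation is Φ(d/√(2P(1−P)/n) − 1.645):
- n = 58: Φ(0.10/0.04047 − 1.645) = Φ(0.826) = 79.6%
- n = 59: Φ(0.10/0.04013 − 1.645) = Φ(0.847) = 80.2%

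So 58 reproduces, and the rounding is minor.

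**Exact behaviour at 58 per arm.** All pairs of binomial counts were enumerated and non-inferiority declared when the one-sided 95% limit excluded a deficit of 0.10. Power is at 95% v 95%. Type I error is at 85% (azithromycin) v 95% (erythromycin), then at its maximum over all pairs of true rates exactly 0.10 apart.

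| Limit or test | Power | Type I error, 85% v 95% | Maximum type I error |
|---|---|---|---|
| Wald (behind the formula) | 79.8% | 6.9% | 15.6% |
| Agresti-Caffo | 77.0% | 5.5% | 7.1% |
| Newcombe | 73.4% | 5.3% | 6.2% |
| Farrington-Manning score | 69.6% | 4.5% | 6.2% |
| Exact unconditional score | 68.2% | 4.1% | 4.8% |

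No row has both 80% power and 5% error. At 59 per arm Farrington-Manning has 73.0% power and 5.0% error at 85% v 95%. Among the even sample sizes checked, about 72 per arm gives 80% exact power with the score or Newcombe limit, and about 76 with the exact unconditional test.

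**A case checkable by hand.** Take 90% v 100%, so the control arm has no failures.
- Wald passes with x azithromycin failures if 0.10 − x/58 > 1.645 × √[(x/58)(1 − x/58)/58]. At x = 3 this is 0.0483 > 0.0478, a pass; at x = 4 it is 0.0310 against 0.0547, a fail. Type I error = P(X ≤ 3), X ~ Bin(58, 0.10), = 0.0022 + 0.0143 + 0.0453 + 0.0939 = 15.6%.
- The score limit takes its variance at the margin: √(0.9 × 0.1/58) = 0.0394. At x = 2, z = 0.0655/0.0394 = 1.66, a pass; at x = 3, z = 0.0483/0.0394 = 1.23, a fail. Type I error = P(X ≤ 2) = 6.2%.

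The Wald error comes from a variance estimated too small when failures are few.

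**Bacteriologic success.** The protocol gives no rate or margin. Assuming equal rates in both arms and the same 0.10 margin, the plan's formula at n = 58 gives 79.6%, 56%, 45% and 38% power for rates of 95%, 90%, 85% and 80%. If both outcomes had to succeed and were independent, joint power would be 0.796 × 0.796 = 63% at 95%, and 0.796 × 0.56 = 45%, 0.796 × 0.45 = 36% and 0.796 × 0.38 = 30% at the lower rates. Without independence, the 95% case lies between 2 × 0.796 − 1 = 59% and 79.6%.

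**The case against.** The best defence is that section 3.6 bases its figure on a printed equation, and on that equation both errors hold to rounding. The 70% belongs to a limit that the protocol does not name, and the choice of interval may sit in an analysis plan not shown here. This stands in part: there is no arithmetic mistake beyond 58.7 written as 58, and no sentence in the document contradicts 80%. It does not rescue the pair of error rates. The limit implied by the equation keeps 80% power only by exceeding 5%, and every limit examined that stays near 5% loses power. Nor do the score-type limits hold 5% everywhere; Newcombe and Farrington-Manning both reach 6.2% at worst.

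Three stronger readings are tempting and unsupported.
- The word equivalence, or a conventional two-sided 95% interval, might suggest that power is really 59% (plan's formula) or about 55% (exact score or Newcombe). Section 3.6 prints 1.645, and 58 reproduces only as a one-sided 5% calculation, so those figures describe designs that were not sized.
- Two primary outcomes might seem to make the stated errors false. Section 3.6 says openly that it sizes clinical success, so the errors refer to that outcome alone.
- A reader might infer inflation to nearly 10% because either outcome could carry the claim. The protocol states no such rule, nor that both must succeed.

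**Conclusion.** The point holds in limited form. For clinical success at 58 per arm, 5% type I and 20% type II error are not obtained together. With the error held near 5%, power is about 70% to 73% with the score-type limits, and 68% with a test that holds 5% throughout. This rests on the plan's own inputs: 95% in both arms, margin 0.10, one-sided 5%. The shortfall against 80% is about 7 to 10 points with the score-type limits.

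The rounding is a minor correction. The missing rate, margin and power for bacteriologic success are a genuine but separate gap: they leave the two-part primary aim without stated power and do not falsify the figures given for clinical success. The 63% joint power holds only if both rates are 95%, the margin is shared and the outcomes are independent. All three are assumptions, and positive correlation between two outcomes of the same infection would raise it.

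**What to change.** In section 3.6:
- State that the 0.10 margin will be judged with a one-sided 95% score-type confidence limit (for example Farrington-Manning), and restate the power at 58 per arm as about 70%.
- Write 59 per arm (118 evaluable), or keep 58 and say that it is rounded down.
- Say that the 5% and 20% apply to clinical success only.

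In section 4.1 and the Primary Aim, either name clinical success as the outcome that decides the claim, or state that both outcomes must succeed, give a rate and margin for bacteriologic success, and say that joint power is lower.

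The cost is a less favourable stated power. Keeping 58 adds no enrolment; 59 adds two evaluable children. Naming one deciding outcome changes the standing of bacteriologic success in the stated aim, so it is a decision for the investigators and more than an edit. Restoring 80% power with a score-type limit would take about 72 per arm (144 evaluable, 28 more), which this fix does not require.

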3.7 Clinical evaluation and laboratory studies

Study patients will be hospitalized for full five days beginning from the time of initiation of study drug therapy. The following clinical and laboratory evaluations will be performed on the study patients at various time period of the study:

- **Weighting:** Before rehydration, after rehydration, just before initiation of the study drug (after the 4-hour observation period), every 24 hours during hospitalization, and at follow-up.
- **History and physical examination:** Before rehydration, after rehydration, at the time of initiation of study drug therapy, daily during hospitalization, and at follow up. In addition to evaluation of hydration status, the history and physical examinations will also focus on adverse events including vomiting, gastrointestinal distress, and rash.
- **Vital signs:** Rectal or oral temperature, pulse and respiratory rates, and blood pressure will be recorded before rehydration, after rehydration, just before administration of study drug, and then every 6 hours during hospitalization.
- **Quantitation of stool volume and/or weight:** This will be done for the rehydration and the observation periods, and for each 6 hour period of hospitalization.

- **Stool character:** Stool will be characterized as follows:
 - Watery:** Stool that can be poured like water
 - Soft:** Stool that cannot be poured, but that takes the shape of the container.
 - Formed:** Stool that retains its shape.
- **Stool culture for *V. cholerae* O1, O139 and non-O1; and *Shigella* and *Salmonella*:** Will be done before initiation of drug therapy on the day of admission, on study day 3, and at follow up 7 days after discharge from the hospital.
- **Rectal swab culture for *V. cholerae*:** Will be done before initiation of the study drug on the day of admission, and daily during hospitalization.
- **Hematologic studies:** Serum electrolytes, creatinine, hematocrit, and serum Sp.gr. will be measured before and after rehydration, and at 24 hours from the time of initiation of study drug therapy. Complete blood count and platelet count will be performed only once, after initial rehydration, however, may also be done at other time(s) if clinically indicated. A total of 2.5 ml + 3.0 ml + 2.5 ml of venous blood will be collected at above specified times.
- **Pharmacokinetics studies:** For determining serum concentration of the study drug, 1.0 ml of blood will be sampled from the first 40 patients enrolled in the study only once- 3, 12, 24 or 48 hours after initiation of study drug therapy drugs. To reduce the number of venipunctures, an indwelling catheter with two way stop cock will be introduced at the time of drawing first blood sample for the study which will be kept in place for a maximum of upto 3 hours, i.e. the earliest time blood will be sampled for pharmacokinetic studies; sampling of blood subsequent to this time will be done by individual pricks. Serum will be separated and stored at - 70°C until assayed. For determination of stool concentration of the study drugs, aliquots of stool (about 5.0 ml) will be sampled from stool collected for each 6 hour period of first 2 days of the study from the same patients, and frozen at - 70°C until assayed.

3.8 Handling of Treatment Failures

If the study treatment is judged to have failed clinically patients will be treated for 3 days with an agent other than azithromycin or erythromycin to which the isolate of *V. cholerae* will be found to be susceptible to. The treatment code will not be broken for these patients. Patients with microbiological failure will be treated with a suitable drug as determined by antimicrobial susceptibility of such isolates.

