Patients eligible for study will be male (1-15 years of age) or female (5-15 years of age), who have watery diarrhea of ≤ 24 hours and signs of severe dehydration (WHO guidelines), and who have cholera vibrios identified on dark-field microscopic screening of stools. Only those patients who have ≥ 20 ml/kg body weight of stool during a 4 hour observation period following initial rehydration period will be entered into the study; only patients from whom *V. cholerae* O1 or O139 is isolated, and who stay in-hospital for three or more days will be eligible for analysis. Written informed consent will be required from the parents/guardians of all children for their inclusion in the study. Patients will be asked to remain in hospital for full five days from the initiation of drug therapy, and to return for a follow-up visit ten days after discharge. Cultures of stool will be obtained on admission to the study, and daily during hospitalization. Stool will be collected, and the volume of watery stool measured for every six hour period of the study. Major outcomes to be compared in the two treatment groups will be clinical success of therapy, defined as resolution of diarrhoea within 96 hours of initiation of study drugs, and bacteriologic success of therapy, defined as the inability to isolate the infecting strain of *Vibrio cholerae* O1 or O139 after 48 hours of therapy. Other outcomes measures examined will be the incidence of adverse reactions to drugs in the two treatment groups, the duration of watery diarrhea and positive stool cultures, and the total volume of watery/liquid stools during study.

Azithromycin is active against multiply-resistant strains of *V. cholerae* O1 or O139, it is safe for use in children, and it is widely available. If single-dose of azithromycin is found to be effective in the treatment of cholera in this study, it will be a considerable advance in treatment of cholera in children; effective single-dose therapy of childhood cholera has not been previously identified with any drug.

Principal Investigator: Last, first, middle: [name]

KEY PERSONNEL (List names of all investigators including PI and their respective specialties)

Name	Professional Discipline/ Specialty	Role in the Project
1. [name]	Internal Medicine	Principal investigator
2. [name]	Internal Medicine	Co-investigator
3. [name]	Pediatrics and Infectious Diseases	Co-investigator
4. [name]	Biochemistry	Research Officer

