4.2 Secondary outcome variables

- Duration of diarrhoea
- Rates of clinical relapse
- Rates of bacteriologic relapse
- Duration of fecal excretion of *V. cholerae*-O1 or *V. cholerae* O139
- Six-hourly, daily and total volume of watery stool during the study period
- Proportion of patients requiring unscheduled intravenous fluids
- Frequency of vomiting and its volume
- Resolution of diarrhoea among patients in two treatment groups on each study day

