7. DEFINITIONS

- 7.1 **Clinical success:** Cessation of watery stool within 96 hours of administration of the study drug without relapse
- 7.2 **Clinical failure:** Continuation of watery stool for > 96 hours
- 7.3 **Clinical relapse:** Cessation of watery stool within 96 hours of administration of the study drugs, its absence for 24 hours or more, and its recurrence anytime during study or between discharge and follow up 7 days from the time of discharge.
- 7.4 **Bacteriological success:** Eradication of the infecting *V. cholerae* organism from fecal specimens within 48 hours of initiation of study drugs without its subsequent isolation
- 7.5 **Bacteriological failure:** Isolation on study day 3 or thereafter from fecal samples of the study patients the same biotype and serotype of *V. cholerae* as was isolated on admission.
- 7.6 **Bacteriological relapse:** Failure to isolate the infecting *V. cholerae* from stool specimen on two consecutive study days, followed by its isolation any time after this, including at the follow-up visit.
- 7.7 **Reinfection:** Isolation of a different biotype or serotype of *V. cholerae* as was isolated on admission, or of the same biotype and serotype with a different antimicrobial susceptibility pattern.
- 7.8 **Duration of diarrhea:** The interval between administration of study drugs to the end of the last 6-hour period the patient had a watery stool.

Facilities Available

Describe the availability of physical facilities at the place where the study will be carried out. For clinical and laboratory-based studies, indicate the provision of hospital and other types of patient's care facilities and adequate laboratory support. Point out the laboratory facilities and major equipments that will be required for the study. For field studies, describe the field area including its size, population, and means of communications. (TYPE WITHIN THE PROVIDED SPACE).

Site: The Research Ward of the Dhaka Hospital of ICDDR,B will be used for hospitalization of the study children. This facility is being used for similar clinical trials for decades.

Study population: The Dhaka Hospital provides treatment to over 110,000 diarrheal patients each year, about 70% of whom are children <15 years of age. Cholera is endemic in Bangladesh, and thousands of children with cholera are treated at this hospital each year; study children will be selected from among them.

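### Analysed children may leave at 72 h or stay to 120 h, yet total stool volume and the relapse window are tied to hospital stay and discharge, not to time from study drug

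*Protocol*

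**What the plan says.** - **Who is analysed.** The project summary asks families to stay five days, but it limits analysis to culture-confirmed patients "who stay in-hospital for three or more days will be eligible for analysis". Three days is thus the threshold for analysis and five days the plan.
- **Length of stay.** Section 3.7: "Study patients will be hospitalized for full five days beginning from the time of initiation of study drug therapy".
- **Stool measurement.** Section 3.7 has stool quantified before treatment "and for each 6 hour period of hospitalization". Nothing is measured after discharge.
- **Volume outcome.** Section 4.2 lists "Six-hourly, daily and total volume of watery stool during the study period". Neither this section nor the secondary-outcome list under Data Analysis says at which hour that period ends.
- **Relapse window.** Section 7.3 counts recurrence during the study or "between discharge and follow up 7 days from the time of discharge". Section 3.7 also puts the follow-up culture 7 days after discharge, whereas the project summary puts the visit ten days after it.
- **Link to the primary outcomes.** Clinical success (7.1) requires no relapse, and bacteriological success (7.4) requires no later isolation. Rectal swabs are daily while the child is in hospital (3.7).
- **Rescue.** Clinical failure (7.2) is "Continuation of watery stool for > 96 hours". Section 3.8 then says "patients will be treated for 3 days with an agent other than azithromycin or erythromycin". It does not say whether this happens on the ward or when a child is judged to have failed.

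**The concern.** Two analysed children with the same illness can be observed for different lengths of time. A child who leaves at 72 h while still purging records a lower total volume than the same child would at 120 h, so leaving early looks like a better result.

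Any child who leaves at 72 h also has two fewer days in which relapse or re-isolation can be found. An undetected event leaves the child counted as a success, so this reaches both primary outcomes. If early leaving were more common in one arm, that arm would look better on total volume and on the success rates for a reason unrelated to the drug.

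Settling the 7-day versus 10-day discrepancy would not cure this, because either number is counted from discharge.

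**Working it through.** The plan gives no figure of its own on this point. Its one computed figure, 58 per arm (section 3.6), is used below only for the expected number of failures. The formula gives 2 × 0.95 × 0.05 × (1.645 + 0.8416)² / 0.10² = 58.74 against the stated 58, and nothing here depends on that rounding.

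**Inputs**
- Shortest stay that is analysed: 3 days = 72 h (project summary).
- Planned stay: 5 days = 120 h (section 3.7).
- Stool measurement period: 6 h, in hospital only (section 3.7).
- Entry threshold for stool output: 5 ml/kg/h (section 3.3).
- Follow-up: 7 days after discharge (sections 3.7 and 7.3) or 10 days (project summary).
- Clinical failure: after more than 96 h (7.2). Rescue: 3 days = 72 h (3.8).

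**1. Measured stool periods per analysed child**
- Leaves at 72 h: 72 / 6 = 12 periods.
- Full stay: 120 / 6 = 20 periods.

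**2. Effect on total volume (illustration: steady output at the entry threshold)**
- 5 × 72 = 360 ml/kg; 5 × 120 = 600 ml/kg; difference 240 ml/kg.
- Steady purging to 120 h is an assumption. The plan expects 95% of children to have stopped by 96 h, so most would lose less than this.
- If early leaving by such children were one percentage point more common in one arm, that arm's mean total would fall by 0.01 × 240 = 2.4 ml/kg. The documents give no rate of early leaving, so no actual bias can be computed.

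**3. End of the relapse and re-isolation window, in days from the dose**

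| Discharge | 7 days after | 10 days after |
|---|---|---|
| Day 3 | 3 + 7 = 10 | 3 + 10 = 13 |
| Day 5 | 5 + 7 = 12 | 5 + 10 = 15 |

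The gap is 2 days in either column.

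**4. In-hospital swabs that can show bacteriological failure (isolation on study day 3 or later, 7.5)**
- Leaves at 72 h: study day 3 only.
- Full stay: study days 3, 4 and 5.

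**5. Rescue against the stay, if failure is judged by 7.2**
- Hours left in the stay once failure is defined: 120 − 96 = 24.
- Share of rescue inside the stay: at most 24 / 72 = 33%, leaving at least 72 − 24 = 48 h outside it.

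**The case against.** **The plan is five days for everyone.** If all children complete it, each gives 120 h and the visit falls on the same day after the dose. That is correct for completers. It does not cover the child whom the three-day rule expressly admits to analysis.

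**Six-hourly and daily volumes are compared as well.** These are fixed windows from the dose and are not distorted in the same way, although the later ones lose the early leavers. This limits the damage but does not repair the total, which is only one of several secondary outcomes.

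**Nothing says that early leaving depends on arm or outcome.** This stands. The design leaves room for bias, but the documents do not show that bias will occur.

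**A reader might go further and infer that rescue itself makes observation time depend on outcome,** with failures kept to 96 + 72 = 168 h and so given more stool periods and a longer relapse window. The documents do not support that:
- No passage keeps a failed child beyond 120 h or requires rescue to be given in hospital.
- Section 7.3 requires "Cessation of watery stool within 96 hours of administration of the study drugs, its absence for 24 hours or more", so a clinical failure cannot also be a clinical relapse.
- Even if the stay were extended to 168 h, the effect on mean observation would be small. At 5% failure (58 × 0.05 = 2.9 children per arm) it is 120 + 0.05 × 48 = 122.4 h. At 15% failure it is 120 + 0.15 × 48 = 127.2 h. Arms that differ by the full 10-point margin would differ by 4.8 h.

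**Conclusion.** The point holds for early leavers against full-stay children. An analysed child may contribute 12 or 20 stool periods and be followed to about day 10 or 12 after the dose (13 or 15 on the ten-day statement). Total volume is therefore not comparable between such children, and the time available to find relapse or re-isolation, on which both primary definitions depend, differs by two days.

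The 360 versus 600 ml/kg contrast assumes steady purging and shows scale only. The size and direction of any bias between arms are unknown, because they depend on how many children leave early and why.

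The rescue question is a separate, smaller matter: sections 3.7, 3.8 and 7.2 leave open how rescue relates to the stay. It should not be read as showing that follow-up time depends on outcome.

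The change is worth making because it is cheap and the follow-up anchor reaches the primary outcomes.

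**What to change.** 1. **Total volume.** Compare total watery stool volume over 0 to 72 h from study drug, which every analysed child completes. Report the total to 120 h separately for children still in hospital. This window precedes rescue for clinical failure as defined in 7.2. It is not shown to precede treatment of microbiological failure, for which section 3.8 gives no start time.
2. **Follow-up.** Set the follow-up visit, and the end of the relapse and re-isolation windows, at one study day counted from study drug for every child, whatever the discharge date. Reconcile the 7-day and 10-day statements at the same time.
3. **Stay and rescue.** The investigators should reconcile the five-day stay (3.7 and the flow chart), the three-day rescue (3.8) and the failure definition (7.2). The clinical rule is theirs to set.

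**Cost.** Wording in the project summary, 3.7, 3.8, 4.2, 7.3, 7.4 and 7.6, and in the secondary-outcome list under Data Analysis. No new visit or measurement is needed, since six-hourly volumes are already recorded and one follow-up visit is already planned. The small downside is that volume after 72 h, including 72 to 96 h within the clinical-success window, leaves the main total.
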